Statistical Considerations:	
Group sample sizes of 23 subjects from a prospective cohort and 23 subjects from historical baseline group will achieve 81% statistical power to reject the null hypothesis of equal means when the population mean difference in neutropenia duration is three days (16 vs 19 days) with a standard deviation for both groups of four days and statistical significance level (alpha) of 0.05 using a one-sided, two sample, equal-variance t-test. Including a 20% drop out rate, we will accrue 29 subjects per cohort.
 
The primary outcome will be analyzed using one-sided t-test with equal variance or the corresponding non-parametric statistical method, depending on the validation of the assumptions.

Estimated Enrollment Period:	36 months
Estimated Study Duration:	60 months

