2.3.2 Exploratory endpoints

- Record pharmacogenomic profiles if results available from next generation sequencing (NGS)/GatorSeq on bone marrow (BM) biopsies for both arms (collected at diagnosis as standard of care).
- Compute ACSS SNP score using the genotype data for subjects in HiDAC 123 arm. We will genotype SNPs of relevance and based on the ACSS score classify into two groups having ACSS score ≥ 0 or <0 . ACSS score will be evaluated for association with certain endpoints (duration of neutropenia, thrombocytopenia, RR and OS). Peripheral blood samples will be collected and analyzed through [name] lab at the University of Florida and NGS results will be used to calculate the ACSS score.
- Describe relapse rate (RR). Relapse rate defined as incidence of confirmed relapse by peripheral blood flow or bone marrow biopsy results. Patients will be monitored up to 48 months after starting induction and will be reported if available.
- Describe overall survival (OS) and leukemia-free survival (LFS). Overall survival defined as the time from date of complete remission (CR) to death from any cause. Leukemia-free survival defined as time from CR to AML relapse or death, whichever comes first. Cause of death will be recorded. Patients will be monitored up to 48 months after starting induction and will be reported if available. These are not expected to be different between the two cohorts.^{1,2}
- Examine minimal residual disease (MRD) positivity after recovery from induction prior to study entry. The following modalities on bone marrow biopsy and aspirate will be used: flow cytometry (FC), karyotyping utilizing cytogenetics (CG), and fluorescence in situ hybridization (FISH). Patients with evidence of disease by any technique above will be classified as being MRD_{pos}. FC will be performed on bone marrow specimens using monoclonal antibodies either as a large panel if the patient was newly evaluated or as a limited but targeted panel based on previously known patient-specific leukemia immune phenotype. MRD will be reported as a percentage of CD45 positive white blood cells (WBCs) and will be labeled MRD_{pos} if leukemic cells account for $\geq 0.1\%$ of the analyzed total WBCs. CG will be performed using standard G-banding methods on 20 metaphase cells. FISH will be reported as a percentage of abnormal nuclei among the examined 300 interphase nuclei. MRD_{pos} by CG will be defined as abnormal karyotype seen in at least

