3. STUDY DESIGN

3.1 Study Overview

This is a single center, open-label, non-randomized phase II study. Twenty nine (29) subjects are planned to be enrolled in this study. Each subject will be administered cytarabine 1000 mg/m² IV q12h x 6 doses on Days 1-3 in the hospital during the consolidation treatment phase. Subject may receive up to four consolidation cycles. Subjects will have laboratory and toxicity assessments as clinically indicated (at baseline, then daily while inpatient and ideally every 48 hours after hospital discharge +/- 24 hours until count recovery from each cycle). These subjects will be compared to 29 historical controls [matched by age (within 3 years), gender (male or female), PS (Karnofsky: 90-100, 70-80, or 50-60) and number of HiDAC cycles received] who received HiDAC 135 from the time period of 2/1/2017-2/1/2019.

Screening data will be reviewed to determine subject eligibility. Subjects who meet all inclusion criteria and none of the exclusion criteria and who have consented will be entered into the study. The following treatment regimen will be used for prospective arm: cytarabine 1000mg/m² IV q12h x 6 doses (Days 1-3) for up to four cycles.

Historical arm subjects will have received cytarabine 1000 mg/m² IV q12h x 6 doses (Days 1, 3, and 5) for up to four cycles from the time period of 2/1/2017-2/1/2019.

Total duration of subject participation will be up to six months from start of first consolidation cycle (each cycle is 28 days, but more time may be required allowing extra time for delayed count recovery in some patients); study participation will end when subject recovers neutrophils and platelets after last administered cycle of chemotherapy, is admitted for conditioning chemotherapy for HCT, dies, or withdraws consent (whichever comes first). However, subjects will be followed every 3 months (\pm 28 days) for up to 48 months after start of induction to determine long-term outcomes. Total duration of the study is expected to be 60 months.

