6) Document supportive care medications (pegfilgrastim or equivalent 48 hours +/- 24 hours after chemo ends; antimicrobial prophylaxis when neutropenic and other anti-infectives needed, eye drops until 48 hours after cytarabine ends, etc.) Supportive care medications and blood transfusions should be documented throughout and for 28 days after last treatment.							
7) Monitoring for SAEs at the time of consent and AEs collection will start the day patient starts cycle 1 of consolidation chemotherapy and continuing throughout the study. Subjects who have received at least one dose of study drug and discontinue prematurely (regardless of reason) will be monitored for any adverse events that occur during study until 28 days following the most recent dose of study treatment or initiation of a new chemotherapy regimen (whichever comes first). If a SAE or AE that is deemed related to the study intervention and ongoing at the end of the monitoring period the event will be monitored until resolution, event returns to baseline or in the investigator's opinion, deems the event is unlikely to resolve due to the patients underlying disease.							
8) End of treatment visit will occur in subjects who complete 3-4 cycles of consolidation or at study withdrawal (for example, at HCT conditioning, relapsed disease or if ended earlier than planned due to toxicity or physician discretion). Other assessments will be performed as necessary by the treating physician. Outside lab results may be collected if subject unavailable to travel to the institution.							
9) All subjects will be followed for long term outcomes until: relapse, death, or until closure of study.							
10) This data may be collected via telephone interview.							
Abbreviations: SOC= standard of care; PRN = as needed; BSA = OS = overall survival; SAE = severe adverse effects, AEs = adverse effects; HCT = hematopoietic stem cell transplant							

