12.3 Analysis of Primary Endpoint

When the required assumptions are met, duration of neutropenia will be analyzed by a one-sided, two sample, equal-variance t-test. If the normal distribution and equal variance are not validated, the corresponding non-parametric method will be used. Primary analysis will be for cycle 1 of consolidation only. Other cycles will be recorded and use descriptive statistics. Further, multivariable linear regression model of the neutropenia in days with group as the primary independent variable of interest will be fitted, while adjusting for some potential confounding variables, including AML type (WHO and FAB), documented infection in consolidation #1 (yes or no), ELN risk category (favorable, intermediate, high) and MRD positivity (yes or no), WBC at diagnosis (<50,000 or \geq 50,000), delay between induction course and consolidation #1 (less than or more than 40 days), allogeneic HCT (yes or no).

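### Study closure cuts prospective follow-up short of 48 months for later entrants, and the relapse rate is a crude incidence with no time horizon, so it is not comparable with the historical controls

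*Combined protocol and SAP*

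**What the plan says.** **Timing.** The synopsis gives "Estimated Enrollment Period: 36 months" and an estimated study duration of 60 months. Section 3.1 repeats the latter: "Total duration of the study is expected to be 60 months". It also has subjects followed every 3 months "for up to 48 months after start of induction to determine long-term outcomes".

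**When follow-up ends.** The sections differ:
- Section 2.3.2: "Patients will be monitored up to 48 months after starting induction and will be reported if available".
- Section 6.1, footnote 9: "All subjects will be followed for long term outcomes until: relapse, death, or until closure of study".
- Section 6.3: contact up to 48 months from induction, or until relapse or death. Study closure is not mentioned.
- Section 8.2: contact until the earliest of relapse, death and 48 months after induction. Closure is not mentioned, and 48 months is not worded as a maximum.

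**Controls.** Section 3.1 takes 29 matched patients "who received HiDAC 135 from the time period of 2/1/2017-2/1/2019".

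**Endpoint.** Section 2.3.2: "Relapse rate defined as incidence of confirmed relapse by peripheral blood flow or bone marrow biopsy results". No time point, censoring rule or treatment of competing death is given. Section 2.3.1 has RR, LFS and OS described in each cohort, and Section 12.5 makes exploratory endpoints descriptive. Cox regression appears only in Section 9.2, for OS by ACSS group.

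**The concern.** A proportion relapsed depends on how long people are watched. If one cohort can be observed for 48 months and part of the other for only 24 to 27, the two proportions answer different questions even when the relapse risk is identical. The shorter window is in the cohort receiving the new schedule, so the pull, taken alone, is towards reassurance.

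Relapse is the plan's check that condensing the schedule does not cost disease control. The synopsis says the site would like to adopt the schedule as standard if the published results are confirmed, and Section 2.3.2 expects no difference in OS and LFS. A crude relapse rate on unequal follow-up is weak support for that expectation.

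**Working it through.** **Inputs.** From the documents: enrolment 36 months; duration 60 months; follow-up cap 48 months from induction; 29 per cohort; controls treated 2/1/2017 to 2/1/2019. Assumed: the 60 months start at first enrolment, and the lead L from induction to enrolment is 0 to 3 months. The nearest guide to L is the 40-day cut point in Section 12.3 for the delay before consolidation 1 (40/30.4 = about 1.3 months). Relapse timing, cured share, death rate and accrual pattern are not in the documents and are shown as ranges.

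**1. The plan's own figure.** Full 48-month follow-up for everyone needs 36 − L + 48 months: 84 at L = 0, 82.7 at L = 1.3, 81 at L = 3. The stated 60 is reproduced only as 36 + 24, that is, 24 months after the last enrolment. That minimum is not written anywhere.

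**2. Who is cut off.** A subject enrolled at month e has potential follow-up min(48, 60 − e + L).
- Latest entry that can reach 48 months: 12 + L, i.e. month 12 to 15.
- Last subject (e = 36): 24 + L, i.e. 24 to 27 months.

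**3. How many.** With even accrual the share below 48 months is (24 − L)/36.

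| L (months) | Share below 48 | Of 29 | Mean potential follow-up |
|---|---|---|---|
| 0 | 66.7% | 19.3 | 40.0 |
| 1.3 | 63.0% | 18.3 | 40.9 |
| 3 | 58.3% | 16.9 | 41.9 |

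Accrual pattern matters. If cumulative accrual follows (t/36)^0.5 (front-loaded), the share is 1 − √((12 + L)/36), or 36 to 42%. If it follows (t/36)^2 (back-loaded), it is 1 − ((12 + L)/36)^2, or 83 to 89%.

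**4. Controls.** The latest control was treated by 2/1/2019, with induction earlier. Every control's 48-month window therefore closed by 2/1/2023, before protocol version 4.0 of April 2023. This is potential follow-up, not follow-up known to have been observed.

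**5. Effect on the crude rate, worked example.** Assume true 48-month relapse of 60% in both cohorts, constant hazard, even accrual and L = 1.5.
- Hazard = −ln(0.4)/48 = 0.0191 per month.
- A share of 13.5/36 = 0.375 reaches 48 months. The other 0.625 is spread evenly over 25.5 to 48 months.
- Mean relapse-free probability in the latter: (e^(−0.0191×25.5) − 0.4)/(0.0191×22.5) = (0.6146 − 0.4)/0.4295 = 0.500.
- Expected prospective rate: 1 − (0.375×0.4 + 0.625×0.500) = 53.8%, against 60% in controls.

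An early-weighted hazard (Weibull, shape 0.7) gives 55.6%.

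**6. Range at even accrual, L = 1.3.** With median relapse time 6 to 36 months, cured share 0 to 40% and competing death 0 to 2% per month, the gap is 0.3 to 6.8 points. That is at most 0.068 × 29 = 2.0 relapses. With no lead, no cure and no competing death the maximum is 7.4 points.

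**7. Outside even accrual.** Take the case giving 6.8 points (median 24 months from enrolment, no cure, no death, L = 1.31) with back-loaded (t/36)^2 accrual.
- A share of (13.31/36)^2 = 0.137 is complete, with relapse-free probability 2^(−46.69/24) = 0.260.
- The rest contribute ∫ 2^(−(60−e)/24) · e/648 de over e = 13.31 to 36, which is 0.332.
- Mean relapse-free probability: 0.137×0.260 + 0.332 = 0.368.
- Expected prospective rate 63.2% against 74.0%: a gap of 10.8 points, or 3.1 relapses of 29.

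Front-loaded accrual makes the gap smaller than in step 6.

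**8. What would cancel it.** The share of control relapses that would have to be missed is the gap divided by the control rate: about 1 to 11% over the step 6 grid (for example 0.065/0.593 = 11%).

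**9. Precision.** At 60% relapse and 29 per cohort, the 95% half-width of a difference is 1.96 × √(2×0.6×0.4/29) = 25 points.

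**The case against.** A reader might infer that 60 months is an arithmetic slip for 84. The documents do not support that. Three places treat 48 months as a ceiling or let closure end follow-up: Sections 3.1 and 2.3.2, and footnote 9 of Section 6.1. Both the enrolment period and the duration are estimates, and 60 reads sensibly as 36 plus 24. What remains is that Section 8.2 states the 48-month rule without a closure clause, so the sections need reconciling.

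A reader might also infer that most prospective subjects fall short and that the raw rate therefore favours HiDAC 123. The first depends on the accrual pattern, which the plan does not give. The second needs equal hazards and equal ascertainment. Control relapses come from records, while prospective subjects are contacted every 3 months. Exclusion J in Section 4.3 requires adequate control records, but its example concerns the period between cycles, not long-term follow-up. Missed control relapses could cancel or reverse the gap. This objection stands against any claim about direction. It does not rescue the crude rate, because it adds a second uncorrected difference between the cohorts.

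LFS and OS are less exposed: both are defined as times from CR, so ordinary survival methods can handle censoring. The plan simply does not name them for the cohort description.

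Finally, the comparison is exploratory and descriptive, and the shift is small beside a half-width of 25 points. That limits the weight of the point. It does not justify an estimator that builds in a known difference in follow-up.

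**Conclusion.** The point holds in a limited form. Not every prospective subject can reach 48 months within 60, the end-of-follow-up rules conflict, and the controls have a full potential window. A crude incidence with no horizon carries that imbalance straight into the cohort description.

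With even accrual, equal hazards and equal ascertainment, the HiDAC 123 relapse rate is lowered by roughly 0.3 to 7 points, at most about 2 relapses of 29. The size depends on relapse timing, cured share, competing death and accrual, none of which the documents give. Strongly back-loaded accrual could take it to about 3 relapses in the least favourable case examined. A demonstrated bias in favour of HiDAC 123 cannot be claimed, since the completeness of the control records is unknown. The primary endpoint (cycle 1 neutropenia), the sample size and the neurotoxicity stopping rule are untouched. The change is worth making because the better method is cheap.

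**What to change.** 1. Keep 60 months. Align the synopsis, Section 3.1, Section 6.1 footnote 9, Section 6.3 and Section 8.2 on one rule: observation ends at 48 months after induction or at study closure, whichever is earlier, with a stated minimum of about 24 months from induction. Extending the study to about 81 to 84 months is not required.
2. In Sections 2.3.2 and 12.5, replace the crude relapse incidence with cumulative incidence, death without relapse being the competing event.
3. Describe LFS and OS by Kaplan-Meier, censoring at last contact or closure. For controls, use the last documented contact and report how complete their follow-up is.
4. Compare the cohorts at a common 24 months from induction. Later estimates can be shown with numbers at risk.
5. Say in the same edit that deaths after relapse are recorded. Footnote 9 and Sections 6.3 and 8.2 end long-term contact at relapse, although Section 8.2 also asks for survival status after the final visit. Censoring OS at relapse would be informative.

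Cost: wording and slightly more analysis. Items 1 to 4 need no data beyond those planned. The horizon for a complete comparison becomes 24 months rather than 48.

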4. SELECTION OF SUBJECTS

Subjects with a clinical diagnosis of de novo acute myeloid leukemia in CR1 who meet the following inclusion and exclusion criteria will be eligible for participation in this study.

4.1 Number of Subjects

Twenty nine (29) subjects are expected to participate in the prospective arm of the study.

4.2 Inclusion Criteria

Subjects must meet all of the following criteria to be eligible for study participation:

- A. Both males and females \geq 61 years of age
- B. A clinical diagnosis of de novo, non-M3 acute myeloid leukemia (AML) confirmed by greater than 20% blasts in peripheral blood or on diagnostic bone marrow biopsy who have completed intensive induction chemotherapy and are confirmed in complete remission #1 (defined by $< 5\%$ myeloblasts on recovery BM biopsy, ANC $> 1000/\mu\text{L}$ and platelets $> 100 \times 10^3/\mu\text{L}$) and able to receive HiDAC consolidation #1
- C. Patients on the prospective arm must be willing to have labs/clinic visits at UF Health Shands approximately every 48 hours +/- 24 hours after discharge from chemotherapy admission to be included
 - If prospective subjects cannot be followed at the UF site then telephone visits are allowed to follow for toxicity and transfusions. Records can be requested from subject's local physician office.
- D. Written informed consent obtained from the subject and the subject agrees to comply with all the study-related procedures. For subjects on the historical arm, there will be a waiver of informed consent (as these patients may be deceased or not be available for retrospective consent).

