2.1.2 Primary endpoint

- To determine duration of neutropenia after HiDAC123 compared to HiDAC 135. Duration of neutropenia is defined as the number of days between first absolute neutrophil count (ANC) < 500 after chemotherapy to day of recovery, defined as first day when ANC > 500 for two consecutive days.

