4.3 Exclusion Criteria

Subjects with any of the following will not be eligible for study participation:

- A. Age < 61 years
- B. Patients unable to provide informed consent for prospective arm
- C. Secondary AML (*documented* history of antecedent hematological disorder, e.g., myelodysplastic syndrome or therapy-related AML) or CML in blast crisis
- D. Patients receiving, received, or who will receive a FLT3 inhibitor
- E. Patients receiving, received, or who will receive an IDH1 or IDH2 inhibitor
- F. SCr greater than 2 mg/dL
- G. Karnofsky PS of 40 or less at study entry
- H. History of any other disease, metabolic dysfunction, physical examination finding, or clinical laboratory finding giving reasonable suspicion of a disease or condition that contraindicates the use of protocol therapy or that might affect the interpretation of the results of the study or that puts the subject at high risk for treatment complications, in the opinion of the treating physician
- I. Prisoners or subjects who are involuntarily incarcerated, or subjects who are compulsorily detained for treatment of either a psychiatric or physical illness

J. For historical arm, subjects will be excluded if adequate data is not available in electronic medical record (e.g., if patient was followed by their local oncologist between chemotherapy cycles and labs/transfusions/clinic notes, etc. are not available)

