6.3 Follow up Evaluations

Subjects will have follow-up visits for the evaluation of adverse events, labs, etc. per standard of care (after discharge from chemotherapy administration, generally every 48 hours +/- 24 hours until neutrophil and platelet recovery after each consolidation chemotherapy cycle). Patients will be evaluated prior to starting next chemotherapy cycle, then admitted for chemotherapy and monitored while inpatient.

If the subject is unavailable to travel to the institution (if situation changes from study inclusion criteria after subject starts first consolidation cycle), the visit may be made via telephone interview to review for adverse event resolution or the occurrence of any new adverse events, and outside labs reviewed if collected. Additionally, medical records may be requested with permission of the subject to complete remote visit reporting e.g., if admitted to an outside institution due to complications of chemotherapy.

If the subject is at the treating facility and the physician decides to hold, reduce, or omit the dose completely, the following procedures should be performed:

- Document reason for delay, decreased or missed doses
- AE assessment
- Hematology laboratory evaluations: complete blood count (CBC) including hemoglobin, hematocrit, white blood cell (WBC) with differential and platelet count

If study therapy is discontinued before planned, disease assessments will be performed as clinically indicated, such as suspicion of relapse. Reason for discontinuation should be documented, e.g., relapse, proceeding to HCT, unexpected toxicity/poor tolerance of chemotherapy, etc. Subjects will continue to be followed every 3 months (\pm 28 days) for survival data up to 48 months after induction chemotherapy is started, or until relapse or death (whichever comes first). Following discontinuation of study therapy for any reason, report the date as appropriate (date of confirmed relapse, date of death, date of start of HCT conditioning, or recovery from last planned or unplanned cycle).

If a subject becomes unreachable during the course of the study, the investigator or study team will make a reasonable effort to contact the subject and document each attempt. If these attempts are not successful, the subject may be declared "lost to follow up." For subjects lost to follow-up, the termination date will be the date of last contact with the subject.

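### Off-site follow-up does not require the ANC values that make up the primary endpoint, so that endpoint can be wholly missing in the HiDAC 123 arm but not among the historical controls

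*Combined protocol and SAP*

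**What the plan says.** **Prospective arm.** Criterion C (synopsis and section 4.2) requires willingness to attend UF for labs and visits about every 48 hours, give or take 24. The synopsis adds that this runs until neutrophils and platelets recover. The sub-paragraph then states "If prospective subjects cannot be followed at the UF site then telephone visits are allowed to follow for toxicity and transfusions", followed by "Records can be requested from subject's local physician office". Section 6.3 covers subjects who become unable to travel after cycle 1 has started. Their visit may be a telephone interview about adverse events, "and outside labs reviewed if collected". Footnote 8 of the Schedule of Events, on the end-of-treatment visit, says "Outside lab results may be collected if subject unavailable to travel to the institution". The Schedule lists the CBC with differential after Day 1 of a cycle only as needed under standard of care, and section 3.1 gives the 48-hour interval as an ideal.

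**Historical controls.** Section 4.3, criterion J: "For historical arm, subjects will be excluded if adequate data is not available in electronic medical record". The example given is "if patient was followed by their local oncologist between chemotherapy cycles and labs/transfusions/clinic notes, etc. are not available".

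**Endpoint and analysis.** Section 2.1.2: "Duration of neutropenia is defined as the number of days between first absolute neutrophil count (ANC) < 500 after chemotherapy to day of recovery", with recovery requiring ANC above 500 on two consecutive days. Section 12.3 bases the primary analysis on cycle 1 and has no rule for a missing ANC or for long gaps between values. Section 8.3 replaces only subjects who received no study drug.

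**The concern.** The primary endpoint consists of two dates, each read from an ANC result. Cytarabine is given in hospital on Days 1-3. Section 1.3 puts the neutrophil nadir from about Days 7-10 and recovery in most patients at Days 21-24; with growth factor, the medians it cites for HiDAC 123 are 14-18 days. Both dates therefore normally fall after discharge, in the period when off-site follow-up applies. A telephone visit can record toxicity and transfusions but cannot produce an ANC, and every route to an outside count is worded as optional.

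The comparison is non-randomized, with 23 evaluable subjects planned per group and a target difference of 3 days. If the cohorts differ in how completely the two dates are observed, that difference enters the treatment comparison directly and cannot be repaired from the data afterwards.

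**Working it through.** **1. The rules side by side, for a subject followed by a local office**

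| Situation | HiDAC 123 subject | Historical control |
|---|---|---|
| Local counts on record, about every 48 h | Kept | Kept |
| Local counts on record, widely spaced | Kept | Kept or excluded, depending on how the undefined term adequate is read |
| No counts obtainable | Stays enrolled, not replaced once dosed, no analysis rule | Excluded under J |

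Only the last row is clearly different between cohorts.

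**2. The plan's own figure.** Inputs from section 12.2: 23 per group, means 16 and 19 days, SD 4, one-sided alpha 0.05, equal-variance t-test.
- SE = 4 × sqrt(1/23 + 1/23) = 1.18 days; noncentrality = 3/1.18 = 2.54; df = 44.
- Power from the noncentral t = 80.5% (normal approximation 81.6%). The stated 81% is reproduced.
- 23/(1 − 0.20) = 28.75, rounded up to 29. The allowance covers 29 − 23 = 6 losses per cohort from all causes.

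**3. Endpoint wholly missing in HiDAC 123 subjects.** Same formula, with fewer evaluable prospective subjects:

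| Evaluable HiDAC 123 | Power, 29 controls kept | Power, matched controls also lost |
|---|---|---|
| 29 | 88.0% | 88.0% |
| 23 | 84% | 80.5% |
| 20 | 81.5% | 75.3% |
| 17 | 78.0% | 69.0% |

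Moderate losses cost little power. Informative loss is the greater risk. In the extreme case where the missing subjects are those with the longest durations, dropping 3 or 6 of 29 lowers the HiDAC 123 mean by about 0.8 or 1.4 days.

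**4. Counts present but sparse.** The documents give neither the off-site share nor the local sampling interval, so both are assumed here. With a count every k days and a random starting day, an event is dated late by (k − 1)/2 days on average: 0.5 days for k = 2 and 3 days for k = 7. Mean error in duration = delay at recovery − delay at onset.
- Weekly at onset, every 2 days at recovery: 0.5 − 3 = −2.5 days.
- Every 2 days at onset, weekly at recovery: 3 − 0.5 = +2.5 days.
- Weekly throughout: 3 − 3 = 0, but the SD rises from about 4.0 to 4.9.

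Shift in the group mean = (number affected/23) × 2.5 days. The error rates below were simulated with 23 per group and everyone else, including all controls, sampled every 2 days:

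| Affected of 23 | Shift in mean (days) | Type I error, weekly at onset only |
|---|---|---|
| 0 | 0 | 5% |
| 2 | −0.22 | 7% |
| 5 | −0.54 | 11% |
| 7 | −0.76 | 14% |

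In the reverse pattern with 5 of 23 affected, power falls from about 79% to 63%, and type I error falls below 5%.

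**The case against.** The strongest reply is that the protocol does not dispense with counts. Criterion C still requires willingness to have labs on the 48-hour schedule, and section 3.1 sets that schedule with no exemption for remote subjects. The version history describes the added synopsis text as concerning lab results collected off site, which suggests the intent was to bring local counts in. Section 7.3.1 ties prophylaxis, and filgrastim where it is used, to the ANC or to count recovery, and Appendix B ties transfusion to blood values. Local offices would therefore probably draw counts around both onset and recovery. The 20% allowance also absorbs some missing endpoints.

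Much of this stands, and it rules out three stronger readings that a reader might infer.
- *That off-site subjects are released from ANC monitoring.* The text does not say so. It leaves collection optional.
- *That the two cohorts follow opposite rules, or that sparse counts arise only under HiDAC 123.* Criterion J keeps a locally followed control whose records are available, and adequate is not defined. Sparse routine-care counts can occur in both cohorts and would tend to cancel if the patterns were alike.
- *That the design favours HiDAC 123, with an 11% false-positive rate to be expected.* That figure needs 5 of 23 subjects to have weekly counts at onset, frequent counts at recovery, and no such pattern among controls. Other patterns give no mean bias or the opposite bias.

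The reply does not show any provision that makes the study team obtain an off-site ANC, or any rule for a dosed subject without one. The wording in section 6.3 about labs if collected applies to subjects who become unable to travel later, but the criterion C sub-paragraph is equally optional for those remote from the start.

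**Conclusion.** The concern holds in a limited form. Followed as written, the protocol can leave the primary endpoint wholly unobserved in dosed HiDAC 123 subjects, whereas a control in that position is excluded. Sparse counts are a risk in either cohort, because no minimum ANC frequency defines adequate data for controls and none is enforced for off-site prospective subjects.

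The direction and size of any bias cannot be read from the documents. The sensitivities run from about −2.5 to +2.5 days per affected subject, with zero mean bias if counts are uniformly weekly, and all rest on an assumed off-site share and sampling pattern. The stated 81% power and 29 per cohort are not in error. This should be corrected because it affects the primary comparison and is easy to prevent while data are being collected.

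**What to change.** 1. In the synopsis, section 4.2 C and section 6.3, state that telephone contact may replace the clinic visit but not the cycle 1 count. State also that the study team must request and record outside CBCs with differential, targeting the existing interval of 48 hours, give or take 24, until recovery.
2. Define one ANC-adequacy rule, for example a maximum gap between values around the fall below 500 and around recovery, and apply it to both cohorts. Use it to give meaning to adequate data in criterion J.
3. In section 12.3, state how a missing ANC endpoint is handled, repeat the primary comparison in subjects who meet the adequacy rule, and report ANC gaps and missing endpoints by cohort.

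No enrolment bar is needed for patients whose local office will not commit to the schedule. That would be a separate trade-off in a single-centre study of 29 subjects.

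The cost is protocol wording and more record requests, which are already permitted. A few subjects in either cohort may fall outside the sensitivity set.
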